#### 8.1.3 Overdose

An overdose is defined as the accidental or intentional administration of any dose of a product that is considered both excessive and medically important.

All occurrences of overdose (suspected or confirmed) must be communicated to Biohaven or a specified designee within 24 hours and be fully documented as an SAE. Details of any signs or symptoms and their management should be recorded including details of any treatments

administered.

Asymptomatic dosing errors (e.g. accidentally taking 2 tablets in one calendar day) should be reported as deviations.

## 8.1.4 Pregnancy

If, following the baseline visit, it is subsequently discovered that a study patient is pregnant or may have been pregnant at the time of the investigational produce exposure, including during at least 6 half-lives after the product administration, the investigational product will be permanently discontinued in an appropriate manner (i.e., dose tapering if necessary for patient safety). Protocol-required procedures for the study discontinued and the follow-up must be performed on the patient unless contraindicated by the pregnancy (i.e., x-ray studies). Other appropriate pregnancy follow-up procedures should be considered if indicated.

The investigator must immediately notify the Biohaven (or designee) Medical Monitor of the event and complete the Pregnancy Form within 24 hours and in accordance with SAE reporting procedures as described in Section 8.1.2. The pregnancy should be reported using paper forms, which should be faxed to

Follow-up information regarding the course of the pregnancy, including perinatal and neonatal outcome and, where applicable offspring information must be reported on a Pregnancy Report Form.

Any pregnancy that occurs in a female partner of a male study participant should be reported to the sponsor. Information on this pregnancy will be collected on the Pregnancy Report Form, as appropriate.

## 8.1.5 Potential Drug Induced Liver Injury (DILI)

Wherever possible, timely confirmation of the initial liver-related laboratory abnormalities should occur prior to the reporting of a potential DILI event. All occurrences of potential DILIs, meeting the defined criteria, must be reported as SAEs as per Section 8.1.2.

Potential drug induced liver injury is defined as:

1. ALT or AST elevation > 3 times the upper limit of normal (ULN)

#### AND

2. Total bilirubin > 2 times ULN, without initial findings of cholestasis (elevated serum alkaline phosphatase)

#### AND

3. No other immediately apparent possible causes of ALT or AST elevation and hyperbilirubinemia, including but not limited to, viral hepatitis, pre-existing chronic or acute liver disease, or the administration of other drug(s) known to be hepatotoxic.

If any potential DILI is identified and meets the criteria above, the Biohaven Medical Monitor (or designee) should immediately be contacted for further instruction and whether the patient must discontinue from the trial and appropriate follow up requirements.

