To closely monitor for potential drug induced liver injury, guidance on reporting potential drug-induced liver injury (DILI) events is provided in the protocol. Lab results that meet predefined LFT abnormality criteria as DILI should be reported as a serious adverse event (SAE). See Section 8.1.5, Potential Drug Induced Liver Injury (DILI).

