## 8.1.2 Collection and Reporting Serious Adverse Events

Following the patient's written consent to participate in the study, all SAEs, whether related or not related to study drug, must be collected, including those thought to be associated with protocol-specific procedures. All SAEs must be collected that occur during the screening period and up to and including the EOT visit. The investigator should report any SAE occurring after these time periods that is believed to be related to study drug or protocol-specific procedures.

An SAE report should be completed for any event where doubt exists regarding its status of seriousness.

If the investigator believes that an SAE is not related to the study drug, but is potentially related to the conditions of the study (such as a withdrawal of previous therapy or a complication related to study procedure), the relationship should be specified in the narrative section of the SAE Report Form.

SAEs, whether related or not related to study drug, must be reported to BHV (or designee) within 24 hours of the site's knowledge of the event. SAEs must be recorded in the EDC system on the AE and SAE electronic Case Report Form (eCRF). If the site cannot access the EDC to report the SAE within the required timeframe, the SAE should be reported using paper forms, which should be

The minimum information required for an initial SAE report is:

- Sender of report (Site number, Investigator name)
- Subject identification (subject number)
- Protocol number
- SAE term (if an SAE is being reported)

If only limited information is initially available, follow-up reports are required. If an ongoing SAE changes in its intensity or relationship to study drug or if new information becomes available, a follow-up SAE report should be sent within 24 hours to BHV (or designee) using the same procedure used for the transmission of the initial SAE.

All SAEs should be followed to resolution or stabilization.

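### Under Protocol 8.1.5, a site's view that another cause is possible removes the automatic rapid notice to the sponsor for a case that meets both liver laboratory criteria

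*Protocol*

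**What the plan says.** Protocol 8.1.5 sets three criteria for potential DILI and joins them with AND.

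1. ALT or AST above 3x ULN.
2. Total bilirubin above 2x ULN, "without initial findings of cholestasis (elevated serum alkaline phosphatase").
3. "No other immediately apparent possible causes of ALT or AST elevation and hyperbilirubinemia". The examples are open-ended and include viral hepatitis, existing liver disease and "the administration of other drug(s) known to be hepatotoxic".

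Two duties depend on the full definition. The first is the report: "All occurrences of potential DILIs, meeting the defined criteria, must be reported as SAEs as per Section 8.1.2". The second is the call: if a case is identified and meets the criteria, "the Biohaven Medical Monitor (or designee) should immediately be contacted for further instruction", including on whether the patient must stop. Laboratory confirmation before reporting is asked for wherever possible.

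On SAEs in general, Protocol 8.1.2 says: "SAEs, whether related or not related to study drug, must be reported to BHV (or designee) within 24 hours". It adds: "An SAE report should be completed for any event where doubt exists regarding its status of seriousness".

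**The concern.** The first two criteria are laboratory facts. The third is a judgment on cause, and only the site is placed to make it before a report is sent. The bar is low: the alternative need only be possible and immediately apparent, not probable. A judgment on cause therefore decides whether the sponsor must be told at once, although elsewhere the protocol wants serious events reported whatever their cause.

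This matters more here than in most studies. Protocol 1.3.4 puts liver test changes first among the adverse events to watch. There is no independent safety committee (10.2). Protocol 6.5 has no liver threshold for stopping; it leaves laboratory abnormalities to the investigator's opinion. The medical-monitor contact in 8.1.5 is thus the one provision that brings the sponsor into the stopping decision at a liver threshold. If criterion 3 removes a case, that step is no longer mandatory. The patient may go on dosing as needed or every other day, with scheduled liver tests 4 weeks apart from Week 4 onward (Tables 1 and 2).

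Entry rules make such a case notable. Patients with AST, ALT or bilirubin above 1x ULN, active hepatobiliary disease, or a history of gallstones are excluded (5.3), so a patient who reaches both thresholds should have started with normal values.

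**Working it through.** No arithmetic applies. The check is to take the reporting rules one by one and ask which of them forces rapid notice on laboratory values alone.

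**Step 1: what the 8.1.5 trigger covers.** Two of its three criteria are laboratory findings and one is attribution. Both duties (SAE report, immediate contact) need all three.

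**Step 2: whether another section sets a laboratory-only trigger.** Protocol 4.1 and the synopsis say: "Lab results that meet predefined LFT abnormality criteria as DILI should be reported as a serious adverse event (SAE"). Each then sends the reader to 8.1.5. Protocol 8.1.1 lists potential DILI as an example of an important medical event, again by reference to 8.1.5. None of these adds a trigger.

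**Step 3: what remains when criterion 3 is not met.**

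| Route | What sets it off | Liver threshold | Deadline |
|---|---|---|---|
| 8.1.1 outcome criteria (such as death, hospitalization) | The outcome, whatever the cause | None | 24 hours (8.1.2) |
| 8.1.1 important medical event | Medical judgment | None beyond the reference to 8.1.5 | 24 hours once called an SAE |
| 8.1.2 doubt rule | Doubt about seriousness | None | 24 hours once reported as an SAE |
| 8.2.2 laboratory abnormality | Judged clinically significant, or led to stopping, interruption or corrective therapy | None | None stated for a non-serious event |
| 6.5 discontinuation | Investigator's opinion | None | None stated |
| 7.2.4 interruption | An AE that requires interruption | None | Consult before restarting |
| 9.4 and 10.2 monitoring | Ongoing sponsor/CRO review | None | None; summaries roughly every 2 months |

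**Step 4: apply the rules to cases.** All four have ALT or AST above 3x ULN and bilirubin above 2x ULN.

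- *No cholestasis, no other apparent cause.* SAE within 24 hours and immediate medical-monitor contact.
- *No cholestasis, another possible cause, hospitalized.* SAE within 24 hours under the general rule. The 8.1.5 contact is not required, but the sponsor hears through the report.
- *No cholestasis, another possible cause, no general SAE criterion met.* Neither duty applies. Notice depends on judgment or on monitoring.
- *Raised alkaline phosphatase at the outset.* Criterion 2 fails, so the case is outside the trigger whatever its cause. This is a separate filter.

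The third case is the gap.

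**Step 5: effect on the endpoint.** The secondary endpoint (Protocol 9.3.2, SAP 4.6.2) counts the laboratory pair with no condition on cause. Criterion 3 cannot lower that count.

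**The case against.** The strongest reply is that the sponsor is not blind. A central laboratory is used, liver tests are done at every scheduled visit, and Protocol 9.4 has laboratory data monitored continuously. Any case with a serious outcome is reported within 24 hours, and a site in doubt about seriousness must report. All of this stands, and it confines the point to cases without a general SAE criterion. It does not restore an automatic trigger. The doubt rule concerns seriousness, and a site content with another explanation may have no doubt. Monitoring has no stated threshold or clock.

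Eligibility narrows the scope for invoking existing liver disease under criterion 3. That stands too, but new viral or drug causes remain possible.

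A fair objection concerns cost. SAE frequency is a primary endpoint (Protocol 3.1), and hepatic-related SAEs are tabulated (SAP 4.6.3.4 and 4.8.2). Widening mandatory SAE reporting partway through a study with sequential enrollment could make earlier and later counts differ. This is right, and the fix below allows for it.

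A reader might infer more than the documents support:

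- *That 4.1 contradicts 8.1.5.* It does not; it is a pointer.
- *That 8.1.2 contradicts 8.1.5.* Its rule on relatedness governs events that are already SAEs.
- *That sites must settle causality before reporting.* Criterion 3 is an initial check on what is immediately apparent.
- *That permitted acetaminophen would be used to set cases aside.* The documents do not call it hepatotoxic; they cap its migraine use and prohibit other use after Baseline (5.4, 5.5). That a site would invoke it is an assumption, and the point does not need it.
- *That notice would be delayed by 2 months.* The documents do not say how fast the sponsor sees individual results, so such a delay is neither shown nor excluded.

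**Conclusion.** The point holds in a limited form. For a case that meets criteria 1 and 2, a site's view that another cause is possible removes both mandatory rapid steps unless a general SAE criterion applies. No other provision in the supplied text forces rapid notice at those laboratory values. The loss is an automatic safeguard for the individual patient. The laboratory secondary endpoint is not biased.

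The size cannot be put as a number of patients, because the documents give no rate for the laboratory pair. What can be stated is the contrast in timing: 24 hours with the trigger, no fixed time without it.

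Two limits apply. The laboratory manual, SAE forms and Investigator's Brochure were not available and may contain a laboratory alert. The SAP rests on protocol Version 6 (SAP 1.1), and the supplied protocol lacks the cohort on CGRP antagonist biologics that SAP 2.1 attributes to that version. It therefore appears to be an earlier one, and 8.1.5 may have changed since. Label: cheap improvement.

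**What to change.** First check how 8.1.5 reads in protocol Version 6. If it is unchanged:

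1. **Medical-monitor contact.** Require it immediately whenever criteria 1 and 2 are met, with confirmation wherever possible as now. Record criterion 3 as a causality item, with concomitant medication details, rather than as a condition for contact. Stopping decisions stay where the protocol puts them. This costs one paragraph in 8.1.5 and some extra calls. It leaves SAE counts and all endpoint definitions unchanged.
2. **SAE report, preferably.** Base the 24-hour report on criteria 1 and 2 as well. State the downside: some added SAE reports that turn out to have another cause, and a change in how a primary endpoint is ascertained. Flag these reports so that SAE counts before and after the change stay comparable. The SAE form guidance needs a matching edit.

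Neither step touches the cholestasis condition in criterion 2. A case with raised alkaline phosphatase would still fall outside the trigger, and the sponsor should confirm that this is intended.

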#### 8.2 Non-serious Adverse Events

A *non-serious adverse event* is an AE not classified as serious.

## 8.2.1 Collection and Reporting of Non-Serious Adverse Events

The collection of non-serious AE information should begin at the initiation of study drug. Non-serious AE information should also be collected from the start of a placebo lead-in phase or other observational period intended to establish a baseline status for a patient.

Non-serious adverse events should be followed until conclusion or stabilization, ore reported as SAEs if they become serious. Follow-up is also required for non-serious AEs that cause interruption or discontinuation of study drug or those that are present at the end of study treatment.

## 8.2.2 Laboratory Test Abnormalities

The following laboratory test abnormalities should be captured on the non-serious AE CRF page or SAE Report Form (paper or electronic) as appropriate:

- 1. Any laboratory test result that is clinically significant or meets the definition of an SAE;
- 2. Any laboratory abnormality that required the patient to have the study drug discontinued or interrupted;
- 3. Any laboratory abnormality that required the patient to receive specific corrective therapy.

#### 9 STATISTICS

#### 9.1 General Procedures

Categorical variables are tabulated with counts and percentages. Continuous variables are summarized with univariate statistics (e.g., n, mean, standard error, median, minimum and maximum).

For the calculation of descriptive statistics of observed data, subjects must have a baseline value to be evaluable for endpoints based on values and changes from baseline over time.

Tabulations of the following endpoints present the number of unique subjects with an event: protocol deviations; interruptions of study therapy; non-study medications; adverse events; and laboratory abnormalities. Thus, for these endpoints, multiple occurrences of the same event are counted only once per subject.

## 9.2 Sample Size

With a sample size of roughly 2000 subjects, and with no events observed, the upper bound of a one-sided, 95% confidence interval for zero observations is roughly 0.0015. Hence, this sample size is large enough to rule out adverse events that occur at rates greater than 15 cases per 10,000 patients.

This study has a subpopulation of approximately 800 subjects with more frequent migraines that is expected to have a greater exposure to the study drug. With this sample size, and no events observed, the upper bound of a one-sided, 95% confidence interval for zero observations is roughly 0.00375. Hence, this sample size is large enough to rule out adverse events that occur at rates greater than 37.5 cases per 10,000 patients.

#### 9.3 Statistical Methods

## 9.3.1 Primary Endpoint(s)

The investigators will determine the intensity of adverse events (AEs) and the relationship of AEs to study therapy. The investigators' terms will be coded and grouped by system organ class using the latest version of the Medical Dictionary for Regulatory Activities (MedDRA) available to the analyst. AEs will be presented by system organ class and preferred term. If a subject had an adverse event with different intensities over time, then only the greatest intensity will be reported. Tabulations will be made for adverse events that occur in at least 5% of

treated subjects, serious adverse events and adverse events leading to discontinuation. Other safety analyses will be described in the statistical analysis plan.

Laboratory abnormalities will be identified from on-treatment laboratory data using a predefined list of clinically significant abnormalities. The number of unique subjects with each abnormality will be tabulated.

#### 9.3.2 Secondary Endpoint(s)

The frequency of subjects that have confirmed values of ALT or AST that exceed 3x the ULN concurrently with confirmed total bilirubin that exceeds 2x the ULN will be tabulated and presented with descriptive statistics and exact confidence intervals.

Both hepatic related AEs and hepatic related AEs leading to discontinuation will be summarized in a manner similar to that described for the primary endpoint.

#### 9.3.3 Demographic and Baseline Characteristics

Tabulations of demographic and baseline characteristics are made for treated subjects. A separate set of tabulations will be made for subjects enrolled but not treated.

## 9.4 Interim Analysis

This is an open label study, single-arm, study designed to evaluate the safety and tolerability of rimegepant. As such, safety monitoring the primary concern. There is little concern, or opportunity, for inflation of type I (false-positive) error. During the course of the study laboratory, safety and exposure data will be monitored on an on-going basis. Summaries of these data will be produced roughly every 2 months for review by the sponsor and CRO. In addition, data may be locked, analyses conducted, and reports produced as required to support safety monitoring, administrative concerns, and regulatory requirements. A clinical study report will be produced after last patient last visit.

#### 10 ETHICS AND RESPONSIBILITIES

#### 10.1 Good Clinical Practice

This study will be conducted in compliance with the protocol, Good Clinical Practice (GCP), Good Laboratory Practice (GLP) and all applicable regulations, including the Federal Food, Drug and Cosmetic Act, U.S. applicable Code of Federal Regulations (title 21), any IEC requirements relative to clinical studies. The study will also be conducted in compliance with the recommendations laid down in the most recent version of the Declaration of Helsinki, with the exception that registration of such Phase 1 trials in a publicly accessible database is not mandatory.

This study will be conducted in compliance with the protocol. The protocol and any amendments and the patient informed consent will receive Institutional Review Board/Independent Ethics Committee (IRB/IEC) approval/favorable opinion prior to initiation of the study.

All serious breaches must be reported to Biohaven (or designee) immediately. A Serious breach is a breach of the conditions and principles of GCP in connection with the stud or protocol, which is likely to affect, to a significant degree, the safety or physical or mental integrity of the patients of the study or the scientific value of the study.

Study personnel involved in conducting this study will be qualified by education, training, and experience to perform their respective task(s).

This study will not use the services of study personnel where sanctions have been invoked or where there has been scientific misconduct or fraud (e.g., lose of medical licensure, debarment).

## 10.2 Data and Safety Monitoring Committee

This study will not make use of a Data Safety Monitoring Committee (DMC). The study medication rimegepant has been tested and found to be well tolerated. Safety will be closely monitored via oversight by the investigators, Sponsor and CRO/designee. Summaries of LFTs and AEs will be reviewed roughly every 2 months by Sponsor/CRO.

#### 10.3 Institutional Review Board/Independent Ethics Committee

The Investigators agree to provide the IEC with all appropriate documents, including a copy of the protocol/amendments, ICFs, advertising text (if any), Investigator's brochure and any other written information provided to study subjects. The trial will not begin until the Investigators

have obtained the IEC favorable written approvals for the above-mentioned study documents. A properly executed written ICF shall be read, signed, and dated by each subject prior to entering the trial or prior to performing any study procedure. The original signed and dated ICF will be kept at the Investigator site and a copy will be given to the subject.

In the event that the protocol is amended, the revised protocol must be approved by the IEC prior to its implementation, unless the changes involve only logistical or administrative aspects of the trial. If a revised ICF is introduced during the study, each subject's further consent must be obtained. The new version of the ICF must be approved by the IEC, prior to subsequently obtaining each subject's consent.

The Principal investigator and the Sponsor's representative must sign the protocol and its amendments (if any) before initiating the study.

It is the Sponsor's responsibility to submit the protocol and its amendments (if any), and the ICFs to regulatory authorities when necessary.

#### 10.4 Informed Consent

Investigators must ensure that patients, or, in those situations where consent cannot be given by patients, their legally acceptable representatives, are clearly and fully informed about the purpose, potential risks, and other critical issues regarding clinical studies in which they volunteer to participate.

Biohaven (or designee) will provide the investigator with an appropriate (i.e., Global or Local) sample informed consent form which will include all elements required by ICH, GCP and applicable regulatory requirements. The sample informed consent form will adhere to the ethical principles that have their origin in the Declaration of Helsinki.

Before the potential subject has undergone any study-related screening procedures, the nature of the study and the potential risks associated with it will be explained to the subject, and the subject will be given an opportunity to ask questions to his or her satisfaction. After the questions are answered, but before proceeding further, the subject must read and sign a written informed consent form. This signed informed consent form will be reviewed and approved by an IRB/IEC, revisions to the protocol and informed consent form will be reviewed and approved by the IRB/IEC, a copy retained in the Study Master File, and the date and time the subject signed the form will be entered in his or her CRF. The subject will be provided with a copy of his or her signed and dated informed consent form.

If informed consent is initially given by a patient's legal guardian or legally acceptable representative, and the patient subsequently becomes capable of making and communicating their informed consent during the study, then the consent must additionally be obtained from the patient.

The informed consent form must also include a statement that Biohaven and its representatives and regulatory authorities may have direct access to patient records.

The rights, safety, and well-being of study patients are the most important considerations and should prevail over interests of science and society.

